4.4 Assessment of Risks and Adverse Device Effects

Risks to the subject will be no greater than those of a standard UDS test. Subjects may experience temporary discomfort upon insertion of the catheters. Test duration may be slightly longer than a standard test while assessment of the study materials is being made, and so discomfort and inconvenience associated with an extended test duration may occur.

Urodynamic testing exposes subjects to risks of urethral instrumentation which can result in infection, urethral trauma and pain (Winters *et al.* 2012). Other risks can include transient discomfort during or following the procedure, transient dysuria or bleeding (hematuria) following the procedure, or urinary tract infection occurs in 2-4% of subjects (Chapple, MacDiarmid & Patel, 2009). Thus, the clinician must weigh the risks and benefits as to whether the urodynamic test offers additional diagnostic value beyond symptom assessment, physical examination and other diagnostic testing (Winters *et al.*, 2012). The risks of radiation exposure during VUDS should also be weighed against the benefits, and explained to the subject (or subject's guardian), however LABORIE does not manufacture radiation-emitting devices and so we do not offer mitigation against these risks.

In conclusion, the overall residual risks associated with the use of T-DOC® 5 French catheters within this study set-up, are acceptable when weighed against the benefits, and are no different than the risks when using other urodynamic catheter technologies. The sponsor team has also established that subjects are subjected to no more than minimal risk since an IDE is not required for this study (Ref: TDOC5Fr-PEDS-01 - Risk Determination). Lastly, UDS and VUDS are widely-performed procedures on pediatric subjects requiring specialized management for urinary incontinence/retention problems, as recommended by the ICS (Abrams *et al.*, 2013), and is useful in characterizing LUT function, identifying causes of symptoms and quantifying related pathophysiological processes (Bauer *et al.*, 2015).

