7.6 Subject Withdrawal

Subjects may withdraw voluntarily from the study or the investigator may terminate a subject's participation (see below). The Investigator will notify the sponsor when a subject is withdrawn from the study (and if possible why), and this will be recorded on the subject's CRF. Subjects who withdraw from the trial will be allowed to be replaced by another subject.

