9.2 Methods of Assessment

A T-DOC® 5 French air-charged catheter will be used to assess and record bladder and abdominal pressures which are in turn used by the clinician to identify urodynamic events. These measurements will be recorded using a LABORIE urodynamics system. The resulting interpretations regarding safety, effectiveness, and usability will be made by the physician overseeing the subject’s case. Patients capable of providing feedback regarding their level of discomfort experienced during the procedure with the T-DOC® 5Fr vesical and abdominal catheters will be presented with copies of the Wong-Baker scale from 0 (“No Hurt”) to 10 (“Hurts worst”) and asked questions by clinic staff who will record their responses on form TDOC5Fr-PEDS-01-CRF4. Subjects will respond to the questions on a scale of 1 through 10.

All study outcome data captured will be compiled and analysed by the LABORIE study team to determine if the endpoints were successfully achieved based on whether the null hypotheses were accepted or rejected.

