11.4 Day 5-7 (Follow-Up)

1. Site personnel will telephone the subject's guardian/caregiver and inquire about any adverse events that occurred after Visit 1 that may or may not be persistent. Record the call details on the subjects' CRF (TDOC5Fr-PEDS-01-CRF1).

NOTE: If an adverse event occurs during this study, any follow-up intervention prescribed is at the discretion of the Investigator. Each subject will be contacted 5-7 days post-test in order to record the occurrence of any adverse events. Any subject with persistent symptoms post-test shall be followed until such a time it is resolved, and the site must notify Laborie of the

outcome of the follow-up. This information should also be recorded on the subject's CRF (TDOC5Fr-PEDS-01-CRF1).

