12.6 Analysis Plan

All subjects enrolled will be considered in the final analysis. Data will be analysed as discussed in Section 12.1 above. A Statistical Analysis Plan containing the details of the analyses and hypothesis testing will be finalized prior to database lock.

If any CRFs are found to be incomplete, the study monitor will follow-up as to the reasoning why. If for some reason a clinical user is unable to complete their questionnaire, the questions they have completed will be included in the analysis. Data will be monitored as the study progresses, please refer to Section 7.7 for details about suspension or premature termination.

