Secondary	
To evaluate the usability of the device by collecting clinical user feedback and evaluating the following subjective measures using defined ordinal scales: ease of use, ease of insertion, presence of artefacts, stability of the tracing, perceived time savings, ease of voiding around catheter, presence of use errors and overall satisfaction.	The usability performance endpoint will be captured in a questionnaire format. The trained clinical users will rate the T-DOC® 5 Fr performance on a scale of 1-5 on the study outcome questionnaire.
Exploratory	
To explore whether the newly designed, smaller sized T-DOC® 5 Fr catheters causes undue discomfort based on subjective subject feedback regarding the discomfort and pain level, for those able to communicate such feedback.	This exploratory endpoint will be measured by collecting patient feedback (within the abilities of the child) regarding the level of discomfort and pain experienced during their Urodynamic test using the Wong-Baker visual analogue scale. Patients capable of providing feedback on a Visual Analogue Scale, will grade their discomfort/pain at 5 or lower, on the Wong-Baker scale from 0 ("No Hurt") to 10 ("Hurts worst").
To explore the effect of several factors (e.g., age, gender, weight, height) on optimal insertion depth of the T-DOC® 5 Fr catheters.	Subjects' age, gender, weight, and height will be recorded on TDOC5Fr-PEDS-01-CRF1. These data will be analysed to determine a subject stratification approach to be used in examining further hypotheses for later research regarding optimal insertion depth.

Analysis revisions from the protocol

All subjects enrolled and completed the urodynamic procedure will be considered in the final analysis. Enrolled subjects who do not undergo the urodynamic procedure or begin the urodynamic procedure but do not complete it (for any reason determined by the investigator to be unrelated to the T-DOC® 5 Fr catheters) will not be included in the final analysis and can be replaced.

Primary Endpoint

In the statistical analysis plan, the null hypotheses for the safety and effectiveness endpoints are designed to rule out success rates $\leq 75\%$. The hypotheses as stated in the protocol are based on obtaining a point estimate of $\geq 95\%$ rather than bounding the lowest rate that would be consistent with the observed data.

The allowable Type I error (α) for each hypothesis will be 5% (1-sided), and the Type II error is calculated to be 10% (90% power).

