Safety and effectiveness will be evaluated separately via the following sets of hypotheses:

Primary Hypothesis for Safety

- H_0 : Clinicians rate T-DOC® 5 Fr vesical and abdominal catheter as safe for measuring urodynamic pressure in $\leq 75\%$ of enrolled pediatric subjects who complete the urodynamic procedure
- H_A : Clinicians rate T-DOC® 5 Fr vesical and abdominal catheter as safe for measuring urodynamic pressure in $> 75\%$ of enrolled pediatric subjects who complete the urodynamic procedure

Primary Hypothesis for Effectiveness

- H_0 : Clinicians rate T-DOC® 5 Fr vesical and abdominal catheter as effective for measuring urodynamic pressure in $\leq 75\%$ of enrolled pediatric subjects who complete the urodynamic procedure
- H_A : Clinicians rate T-DOC® 5 Fr vesical and abdominal catheter as effective for measuring urodynamic pressure in $> 75\%$ of enrolled pediatric subjects who complete the urodynamic procedure

The study will be declared a success if both null hypotheses for safety and efficacy are ruled out.

Secondary Endpoint

In the statistical analysis plan, adjustments are made to the approach that will be followed to evaluate the secondary endpoint to reflect that the goal is to qualitatively describe users' interactions with a device as described in regulatory guidance for usability testing (*FDA's guidance- 'Applying Human Factors and Usability Engineering to Medical Device's, 2016*). Clinical users who have performed three or more procedures with the T-DOC® 5 Fr catheters, shall rate the T-DOC® 5 Fr catheter usability performance on a scale of 1-5 for the clinical user questionnaire, comparing their experience with use of their currently used uroynamics catheter. Responses of 3, 4, or 5 will be tallied as a positive result while responses of 1 or 2 will be tallied as a negative result.

Since there will be 5 responses at most for each of the questions for the secondary endpoint, and the results are thus not well-suited to statistical analysis, hypothesis testing is not appropriate. Instead, the proportions of positive and negative results will be summarized and analysed using descriptive statistics.

Exploratory Analysis

Exploratory Analysis for Discomfort/Pain

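### The SAP tests safety on completers only, so a catheterised child whose test stops for a reason judged unrelated to the device leaves the only planned safety analysis

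*SAP*

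**What the plan says.** Protocol 12.6 sets the analysis population as everyone enrolled: "All subjects enrolled will be considered in the final analysis". The SAP openly revises this under Analysis revisions from the protocol. Two groups are removed: enrolled children who never undergo the procedure, and children who "begin the urodynamic procedure but do not complete it (for any reason determined by the investigator to be unrelated" to the 5 Fr catheters. Both groups "will not be included in the final analysis and can be replaced".

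The SAP's safety and effectiveness hypotheses then carry the same restriction, to the proportion "of enrolled pediatric subjects who complete the urodynamic procedure". No separate exposed or as-treated set is defined for safety. Success requires both null hypotheses to be rejected.

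Four other provisions bear on the point:

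- Protocol 4.4, on the source of harm: "Urodynamic testing exposes subjects to risks of urethral instrumentation which can result in infection, urethral trauma and pain".
- Protocol 11.3, on sequence: catheters are placed at step 7 and the urodynamic study is run at step 8.
- Protocol 11.4, on follow-up: "Each subject will be contacted 5-7 days post-test in order to record the occurrence of any adverse events".
- Protocol 7.6, on replacement: "Subjects who withdraw from the trial will be allowed to be replaced by another subject". It sets no condition about whether the child was already catheterised.

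**The concern.** The exclusion makes sense for effectiveness. If a pump or processor fails, the catheter's ability to measure pressure was never tested.

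It does not carry over to safety. On the protocol's own account, exposure to harm begins with instrumentation, not with a finished test. The excluding judgement concerns why the test stopped, which is a different question from whether the child was harmed. A child could have both catheters placed, stop because of an equipment fault, and have haematuria that is noticed afterwards. That child meets the exclusion wording.

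The judgement is made without blinding (12.5), without a data monitoring committee (17.3), and with no deadline in the SAP, so it may be made once an outcome is known. At stake is one of the two co-primary claims: as written, it describes completers rather than children exposed to the device.

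**Working it through.** **Inputs.** Null rate 75% and one-sided alpha 5% (SAP, Primary Endpoint). Minimum 28 and maximum 33 subjects (Protocol 7.4). The protocol's minimum reproduces: ln(0.05)/ln(0.90) = 28.43, stated as 28. The SAP does not name its test. I assume the exact binomial test, since the protocol works from the binomial distribution. The documents give no non-completion rate, so the numbers of restored children below are assumptions.

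**Formula.** p = P(X ≥ x | n, 0.75) = Σ C(n,k) 0.75^k 0.25^(n−k), for k = x to n. Reject the null if p ≤ 0.05.

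For x = 26, n = 28 the terms for k = 26, 27, 28 are 0.01333 + 0.00296 + 0.00032 = 0.0166.

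**Restoring excluded but exposed children to the safety denominator:**

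| Analysed completers | Restored | Exposed set | p | Result |
|---|---|---|---|---|
| 26/28 (p=0.0166, pass) | 1 not safe | 26/29 | 0.0455 | pass |
| 26/28 | 2 not safe | 26/30 | 0.0979 | fail |
| 27/28 (p=0.0033, pass) | 2 not safe | 27/30 | 0.0374 | pass |
| 27/28 | 3 not safe | 27/31 | 0.0828 | fail |
| 28/28 (p=0.0003, pass) | 3 not safe | 28/31 | 0.0307 | pass |
| 28/28 | 4 not safe | 28/32 | 0.0698 | fail |
| 25/28 (p=0.0551, fail) | 1 safe | 26/29 | 0.0455 | pass |

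A pass turns into a failure at two, three or four restored not-safe children, depending on the completer result. All of these fit within the 33 − 28 = 5 extra places. The last row shows the reverse: the rule can also cost the sponsor a success.

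**Consistency of the SAP with itself.** The revisions paragraph excludes a started-but-incomplete child only if the reason is unrelated to the catheters, which implies that a device-related non-completer stays in. The endpoint table and the hypotheses cover only children who completed. Read literally, those would leave out even a child whose procedure stopped because of the catheter.

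**Whether another analysis covers the gap.** Adverse events go on the CRF (Protocol 10.2), serious ones are reported (10.3), and persistent symptoms are followed to resolution (11.4). The SAP mentions adverse events only among the data listed for the insertion-depth analysis. It plans no adverse-event table or other safety analysis.

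**The case against.** The strongest reply is that the scenario is rare and the harm is not hidden. Much of this stands.

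- **Capture.** An excluded child still has adverse events recorded, reported and followed. The loss is confined to the primary safety test and the claim drawn from it.
- **Likelihood.** Reversing a 26/28 pass takes two children who were catheterised, stopped for a non-device reason, and were not safe. One is not enough. The only harm rate given is 2-4% for urinary infection (4.4). If all five spare places were such children, the chance of two or more infections is 1 − (1−r)^5 − 5r(1−r)^4, which is 0.4% at r = 0.02 and 1.5% at r = 0.04. Other harms would raise it, but the table shows what is possible, not what is expected.
- **Catheter-caused stopping.** If pain or injury from the catheter stops the test, the reason is device-related and the exclusion clause does not apply. Only harm separate from the stopping reason is affected, subject to the SAP inconsistency above.

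A reader might infer three stronger things that the documents do not support:

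1. That the rule can only raise the observed safe rate. It also removes children who were never exposed, which is proper, and it can remove exposed children who were safe, as 25/28 against 26/29 shows.
2. That the person who rates safety also decides the exclusion. The SAP names the investigator. Protocol 9.2 says "The resulting interpretations regarding safety, effectiveness, and usability will be made by the physician overseeing" the case. At one or two sites these may be the same person, but this is not stated.
3. That harm reported at the 5-7 day call would count as not safe if the child were kept in. Protocol 10.6 links the safety endpoint to adverse events at the visit and at follow-up, but nothing says when the rating is made or that the call can change it. If the rating is fixed on Day 1, late harm is missed for completers too.

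**Conclusion.** The concern holds as a defect in how the primary safety set is defined. A single completer-based set serves both tests. An exposed child can leave the only planned safety analysis, and be replaced, on an unblinded and undated judgement about why the test stopped. The direction of the resulting bias is uncontrolled rather than known.

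In a set of 28, two exclusions can decide the result at the pass mark (26/28 to 26/30), and one can decide it in the other direction (25/28 to 26/29). These figures rest on an exact one-sided 5% binomial test and on assumed counts. The change should be made because a better set is available at little cost, not because the documents show that children have been or will be wrongly excluded.

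**What to change.** 1. Test safety on every child in whom insertion of either 5 Fr catheter was attempted, whatever the reason for stopping. Reword the safety hypotheses to match.
2. Keep the device-unrelated exclusion for effectiveness only.
3. State in Protocol 7.6 and the SAP that a replaced child with an attempted insertion stays in the safety set, gets a safety rating, and gets the planned 5-7 day call unless consent for contact is withdrawn. The rating must be required explicitly: Protocol 13.3 leaves missing values missing, so an unrated child would drop out again.
4. State that the safety rating is finalised after that call.
5. Reconcile the SAP's revisions paragraph, which implicitly keeps device-related non-completers, with its endpoint table and hypotheses, which cover completers only.

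**Cost.** SAP wording, which the SAP allows to be revised before database lock, and a short change to 7.6, which goes to the IRB under Protocol 16. The calls are already planned for each subject. A safety rating is needed for the few non-completers, because the SAP's endpoint text limits ratings to completers. The safety and effectiveness denominators may differ by a few children, and the safe rate may be slightly less favourable.

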7.4 Recruitment Plans

The target enrolment is a minimum of 28 subjects up to a maximum enrolment of 33 subjects. A minimum of 10 male patients and 10 female patients shall be recruited so that insertion depths and any usability issues identified with one or both genders can be reliably identified.

Subjects who are visiting the urodynamics clinic for their medically-indicated urodynamics test will be approached regarding participation in this study. It is estimated that recruitment will be 3 subjects per week, therefore it should take approximately 9-12 weeks to recruit 28-33 subjects. Recruitment will be monitored through scheduled meetings with the site co-ordinator. If the subject and legal guardian sign the informed consent, this will be treated as the point of enrolment.

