12.3.2 Exploratory Data Collection regarding influencing factors on insertion depth

To satisfy the second exploratory endpoint, subject data including gender, age, height, weight, adverse events during or immediately following the test and 5-7 days follow-up, catheter insertion depth will be collected as objective evidence on each patient's CRF, where insertion depth is considered the response variable and assumed to be influenced by gender, age, height, weight and/or BMI. Adverse event data will be factored into the assessment of the adequacy of the individual insertion depth used during the subject's procedure.

The collected data will be reported using graphical tools for central tendency and dispersion of insertion depths based on gender, age, height, weight, and BMI. The goal of reporting data in this manner is to facilitate the identification of a natural subject stratification approach for use in later research regarding optimal insertion depth.

Based on the stated data collection and analysis approach, the anticipated outcome of this endpoint, and the fact that the subject population is not being controlled for age, height, or weight, this study exploratory objective is being evaluated as a case-series observational study. Accordingly, sample size will not be pre-determined based on pre-ordained confidence and reliability statements.

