To satisfy the first exploratory endpoint (subject experience), a categorical response variable using the Wong-Baker scale from 0 ("No Hurt") to 10 ("Hurts worst") will be used. Subjects will grade their discomfort/pain on the Wong-Baker scale from 0 ("No Hurt") to 10 ("Hurts worst"). of 1, 2, 3, 4, or 5 will be tallied as a positive result while responses of 6, 7, 8, 9, or 10 will be tallied as a negative result.

Because the subjects range in age from 2-12 years, the number of subjects capable of providing feedback on the Wong-Baker scale is anticipated to be limited (≤ 10 is expected). Due to this uncertainty, no formal hypothesis testing will be performed. However, the binary endpoint described above as well as the mode and frequency distribution of the Wong-Baker scale will be used to summarize the results.

Exploratory Analysis for Insertion Depth

To satisfy the second exploratory endpoint, subject data including gender, age, height, weight, adverse events during or immediately following the test and 5-7 days follow-up, catheter insertion depth will be collected as objective evidence on each patient's CRF, where insertion depth is considered the response variable and assumed to be influenced by gender, age, height, weight and/or BMI.

Regression testing can be used to examine the relationship between the insertion depth and collected data (gender, age, height, weight and BMI). The collected data will also be reported using graphical tools based on gender, age, height, weight and BMI. T-tests for differences in insertion depth based on subgroups (male and female, above and below the median height, weight and BMI) will be performed if appropriate.

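### Regression of insertion depth is optional and unspecified, while the named t-tests split body size at the median and compare the sexes without adjusting for size

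*SAP*

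**What the plan says.** The SAP, under Exploratory Analysis for Insertion Depth, takes insertion depth as the response and lists three tools.

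- **Regression, permitted.** "Regression testing can be used to examine the relationship between the insertion depth and collected data", the data being sex, age, height, weight and BMI. It does not say whether covariates enter jointly or singly, in what functional form, or for which catheter.
- **Graphs, committed.** "The collected data will also be reported using graphical tools based on gender, age, height, weight and BMI".
- **T-tests, conditional.** The tests named are "T-tests for differences in insertion depth based on subgroups (male and female, above and below the median height, weight and BMI"), and the SAP says of them that they "will be performed if appropriate". No criterion for appropriateness is given, age is not among the splits, and no size adjustment is mentioned for the sex comparison.

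Protocol 12.3.2 planned graphical reporting only. It treats the objective as an observational case series with no pre-set sample size, partly because of "the fact that the subject population is not being controlled for age, height, or weight". Its aim is a natural way to stratify subjects in later research. Protocol 7.4 fixes the numbers: "The target enrolment is a minimum of 28 subjects up to a maximum enrolment of 33 subjects", and "A minimum of 10 male patients and 10 female patients shall be recruited", the latter partly so that insertion depths can be reliably identified by sex.

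**The concern.** Protocol 3.3 and 7.1 admit children from birth to 12 years. A median split of height puts an infant and a child just under the median in one group, and treats two children on either side of it as different. The cut-point is a feature of the 28 to 33 children who happen to be enrolled, so it is a weak candidate for a natural stratum.

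The SAP itself assumes that depth depends on both sex and size. A sex comparison that ignores size estimates the sex effect plus whatever size difference exists between the boys and girls enrolled. If the sexes are balanced on size it is unbiased, but less precise than it could be.

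At stake is the quality of the hypotheses passed to later research: a relation with size could be missed, or a sex difference reported that is really one of height. The permitted regression could prevent both. However, one-covariate-at-a-time fits would also meet the SAP's wording and would leave sex unadjusted.

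**Working it through.** The documents give no test level, effect size, SD or power for insertion depth, so there is no figure of the plan's own to reproduce.

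**Inputs from the documents.** N = 28 to 33 and at least 10 per sex (protocol 7.4), so sex splits from 14:14 to 18:10 (N = 28) or 23:10 (N = 33). No control of age, height or weight (protocol 12.3.2).

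**Assumptions, not from the documents.** Two-sided 5% tests, linear size effect, normal errors, depth–size correlation 0.4 to 0.8, height difference between the sexes 0 to 1 SD.

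**1. Information kept by a median split.** For a covariate x with unit variance, centred at its median, the squared correlation between x and its split indicator is (E|x|)².
- Normal x: E|x| = √(2/π) = 0.798, squared 0.637, so the loss is 36%. Effective N is 28 × 0.637 = 17.8, or 33 × 0.637 = 21.0.
- Uniform x: E|x| = √3/2 = 0.866, squared 0.75, so the loss is 25%. Effective N is 28 × 0.75 = 21, or 33 × 0.75 = 24.75.

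This applies to the height, weight and BMI splits only. Sex is already binary and loses nothing by being split.

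**2. Power, N = 28, by simulation.** Normal covariate:

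| Correlation | Continuous | Median split |
|---|---|---|
| 0.4 | 58% | 39% |
| 0.5 | 80% | 58% |
| 0.7 | 99% | 92% |
| 0.8 | 100% | 99% |

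With a uniform covariate at correlation 0.5 the figures are about 81% and 66%.

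**3. Sex t-test with no true sex effect.** Its bias, in SDs of depth within each sex, is correlation × height difference: 0.5 × 0.5 = 0.25, and 0.8 × 0.5 = 0.40. Simulated rejection rates over correlations 0.5 to 0.8 and the three sex splits above:

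| Height difference | Unadjusted | Adjusted for height |
|---|---|---|
| 0 | 5% | 5% |
| 0.25 SD | 6–8% | 5% |
| 0.5 SD | 9–18% | 5% |
| 1 SD | 23–54% | 5% |

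**4. Sex t-test with a true effect of 0.8 SD, 14:14, no height difference.** Power is about 53% unadjusted. With height in the model it is about 63% at correlation 0.5, 79% at 0.7 and 91% at 0.8. The no-imbalance condition matters: with a 0.5 SD height difference in the same direction and correlation 0.8, the figures are about 86% and 89%, because bias then helps the unadjusted test to reject.

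The simulated figures carry an error of up to about one percentage point.

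**The case against.** The strongest reply is that the paragraph already contains the remedy. The regression it permits names sex and every size variable; fitted jointly with continuous covariates, it would lose no information to splitting and would adjust sex for size. The graphs are committed and can show the continuous relation. The t-tests come last and are conditional. A reader might infer that depth will be compared by t-tests alone and that information will therefore be wasted; the SAP does not say that. What remains is that the regression is neither required nor defined.

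A reader might also infer that sex is confounded with body size in this trial. The documents give no size distribution by sex, and the protocol's remark that size is not controlled says nothing about imbalance between boys and girls. Confounding is a risk whose size is unknown.

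The least favourable figures also belong to different settings. At correlation 0.8, plausible over so wide an age range, the split costs about one point of power. At 0.4 to 0.5, where it costs about 20, a 0.5 SD imbalance gives the sex test a rejection rate of only about 7–10%. These points stand.

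Finally, protocol 4.3 makes the objective hypothesis-generating, and a grouped display partly suits an aim of finding strata. Protocol 3.3 says recorded insertion depth will feed into labelling, but neither document says that the t-test strata will. That limits the seriousness without making an uncommitted model preferable to a committed one.

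**Conclusion.** The point holds in a limited form. The SAP leaves the better analysis optional and undefined, and names t-tests that are weaker for three size measures and unadjusted for sex. If those tests carry the analysis, each median split loses about a quarter to a third of the information (25–36%). The effect on power ranges from large at correlations of 0.4 to 0.5 to negligible at 0.8. The sex comparison ranges from valid but imprecise, with no size imbalance, to a rejection rate of about 9–18% at a 0.5 SD imbalance. All these figures rest on the linear, normal, two-sided 5% set-up and on assumed correlations and imbalances.

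Severity is low. The SAP defines study success by the two primary hypotheses alone, and nothing in this analysis can change that outcome.

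**What to change.** Replace the permission with a commitment in the SAP:

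- Fit a linear regression of insertion depth on continuous height (or age) plus sex, separately for the vesical and abdominal catheters, since each child receives both (protocol 8.1). Take the sex effect from this model.
- Fit weight and BMI as alternative continuous predictors, one at a time. Age, height, weight and BMI are collinear, and 28 to 33 children will not separate them in one model.
- Report slopes and the adjusted sex difference with 95% confidence intervals, beside scatter plots.
- Keep any median-split or unadjusted sex summaries as description only.

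The cost is SAP wording. Protocol 11.3 already records weight, height, date of birth, sex and insertion depth, and the SAP allows revision before database lock. One thing to confirm is that the case report form holds a depth for each catheter, because the protocol refers to insertion depth in the singular. If only one was recorded, the report should say which.
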